#### Panel 6 C-SSRS Scores

C-SSRS Score	Related to:
1 Wish to be dead	Suicidal ideation
2 Non-specific active suicidal thoughts	
3 Active suicidal ideation with any methods (not plan) without intent to act	
4 Active suicidal ideation with some intent to act, without specific plan	
5 Active suicidal ideation with specific plan and intent	
6 Preparatory acts or behaviour	Suicidal behaviour
7 Aborted attempt	
8 Interrupted attempt	
9 Non-fatal suicide attempt	
10 Completed suicide (only applicable for the post-baseline assessments)	

In the C-SSRS, non-suicidal self-injurious behaviour is captured as a different behaviour; patients may have reported non-suicidal self-injurious behaviour in addition to suicidal ideation/behaviour. Positive responses to non-suicidal self-injurious behaviour will be summarised separately.

For patients with any post-baseline suicidal behaviour (C-SSRS scores of 6 to 10), listings will be prepared including all C-SSRS scores; C-SSRS scores related to suicidal behavior will be flagged.

All assessments will be regarded as valid for C-SSRS.

Missing C-SSRS scores will not be imputed.

### **12.6.2 Paediatric Adverse Event Rating Scale (PAERS)**

Note, all assessments will be regarded as valid for PAERS (that is, the criteria that assessment date-date of last IMP must be  $\leq 7$  days will not be applied).

For each item, a severity score will be derived where the analysis value is defined as:

- If *Recently Present*=No, the analysis value will be *Absent*.

Otherwise, the analysis value will be the reported Severity (*Mild*, *Moderate*, *Severe*, or *Extreme*)

The assessments for the PAERS will be prepared according to the description in the [Data Handling Plan](#). For each item 1 to 43, the following parameters will be derived for each analysis phase following a baseline (all assessments within a phase will be included in the evaluation):

- *Worst severity score*:  
Worst severity score of the item (analysis value will be the worst severity)
- *Worsening of severity score compared to baseline*:  
Worsening of the item compared to OLEXA (analysis value will be ‘Yes’ or ‘No’)

If a patient had a worsening of an item, all original assessments at the OLEXA will be listed.

Also graphical presentations of the PAERS will be done.

Item 44 and 45 will only be listed, based on APES.

For further details, see [Data Handling Plan](#).

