9.4.9 Assessment Tools

9.4.10 Paediatric Adverse Event Rating Scale (PAERS)

The PAERS³⁴ is a clinician-rated scale designed and validated to assess adverse events occurring in paediatric patients who are treated with psychotropic medication in clinical studies.

The PAERS consists of 45 items: 43 specific signs and symptoms and two to be specified. Each item specifies if the adverse event was present recently, if it was resolved (No, Yes), related to drug (No, *Study drug, Other drug, Drug-drug interaction*), its severity (*Mild, Moderate, Severe, Extreme*) and if it impaired function (No, Yes).

The PAERS can be administered by a clinician after a short training session. It takes approximately 10 minutes to administer and score the PAERS.

The PAERS must be applied after the non-leading, open questions on any adverse events (see section 9.4.1). As this recording of adverse events should precede the use of the PAERS, the numbers of adverse events captured by these two methods potentially differ.

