17.10 Safety Analyses

17.10.1 Analysis of Adverse Events

Adverse events will be classified according to the time of onset of the adverse event:

- *lead-in adverse event* – an adverse event ongoing from lead-in study 12709A or study 12710A and prior to the date of first dose of IMP in study 12712A
- *treatment-emergent adverse event* (TEAE) – an adverse event that starts or increases in intensity on or after the date of first dose of IMP in study 12712A.

Adverse events, sorted by system organ class (SOC) and preferred term, will be summarised.

TEAEs may be allocated into study periods (these will be defined in the *Statistical Analysis Plan*).

The primary objective will be addressed with an overall clinical evaluation of the safety results.

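### The PAERS listing for patients whose item worsened is limited to the OLEXA visit, so it leaves out the worsened record; post-OLEXA relatedness, resolution and functional impairment for items 1–43 have no stated output.

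*SAP*

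**What the plan says.** PAERS is a named component of the primary endpoint (Protocol 16.1, SAP 3.1). There is no hypothesis test behind that endpoint: "The primary objective will be addressed with an overall clinical evaluation of the safety results" (Protocol 17.10.1).

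Protocol 9.4.10 describes 45 items, of which 43 are specific signs and symptoms. For each item the rater records whether it was recently present, whether it resolved, and whether it was "related to drug (No, *Study drug, Other drug, Drug-drug interaction*), its severity (*Mild, Moderate, Severe, Extreme*) and if it impaired function (No, Yes").

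SAP 12.6.2 reduces each item to a severity value. An item not recently present is scored as absent. "Otherwise, the analysis value will be the reported Severity". For items 1–43 two parameters are then derived from all assessments in each phase after a baseline: the worst severity, and a yes/no flag described as "Worsening of severity score compared to baseline", the baseline being OLEXA.

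The section then gives the listing rule: "If a patient had a worsening of an item, all original assessments at the OLEXA will be listed". It adds "Also graphical presentations of the PAERS will be done", without saying what the graphs will show, and it lists items 44 and 45 with no restriction to OLEXA. For details it refers to the Data Handling Plan.

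**The concern.** A worsening relative to OLEXA can only occur after OLEXA. A listing triggered by worsening but confined to OLEXA shows the state before the event and omits the event itself.

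This listing is also the only place in the SAP where the original PAERS records for items 1–43 would be shown, as opposed to values derived from severity. If it prints the wrong visit, the other fields collected at each rating drop out of the stated reporting.

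The study is open-label with no concurrent control, and its primary objective is met by clinical judgement of the safety data. A reader of a PAERS worsening will want to know whether the rater attributed it to study drug, whether it impaired function and whether it went away. The OLEXA record cannot answer that. Under footnote e of the flow chart it is the rating from the lead-in completion visit, made before extension treatment started.

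**Working it through.** There is no planned figure to reproduce. The check is a count of ratings and a comparison of fields collected with outputs planned.

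**1. What OLEXA means.** The SAP abbreviation list gives it as baseline extension A. SAP section 2 calls it the baseline visit, identical with Visit 12 of the lead-in study. SAP 18.1 assigns lead-in Visit 12 as OLEXA for assessments made in the lead-in studies, and Visit 1 of 12712A otherwise. On any of these it is a single pre-treatment time point.

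**2. Count of scheduled ratings.** SAP Appendix II, Table 1 schedules PAERS at Visits 1 to 13. Protocol 8.3 confirms it for the telephone visits.

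- OLEXA: 1 (Week 0)
- After OLEXA: Weeks 1, 2, 3, 4, 6, 8, 10, 12, 15, 18, 22 and 26 = 12
- Total: 1 + 12 = 13

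Read literally, the rule lists 1 of 13 for a completer and 0 of the 12 among which a scheduled worsening must fall. Patients who withdraw have fewer ratings. Unscheduled site visits requested at telephone contacts add more, since Protocol 8.3 requires PAERS there too. The share of post-OLEXA records listed is zero in every case.

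**3. Fields against outputs, items 1–43, after OLEXA.**

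| Field collected | Output stated in protocol or SAP |
|---|---|
| Recently present | Yes, as absent or not within the severity value |
| Severity | Yes: worst severity, worsening flag, graphs (content unspecified), probably by-visit summaries under SAP 12.2 |
| Resolved | None stated |
| Related to drug | None stated |
| Impaired function | None stated |

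Of five fields, two feed the severity value and 5 − 2 = 3 have no stated output.

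**4. A worked record.** Take an item absent at OLEXA; severe, related to study drug and impairing function at Week 6; and resolved at Week 8. Worst severity becomes Severe and worsening becomes Yes. The listing shows one row: OLEXA, not recently present. The Week 6 and Week 8 records are not listed.

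**5. Whether another PAERS or general safety output fills the gap.** SAP 12.2 also provides a listing of all values, but a potentially clinically significant (PCS) value triggers it. Appendix IV defines PCS criteria only for laboratory tests, ECG, vital signs and body measurements, so a PAERS item cannot trigger it.

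**6. Comparison with the SAP's other patient-level listings.** The PCS listing (12.2) gives all values of the variable for the affected patient, with flags. The liver listing (12.3.3) gives all available values in date order. The C-SSRS listing (12.6.1) gives all scores, with the behaviour scores flagged. PAERS is the exception, and SAP section 17 does not record it as an intended change.

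**The case against.** The strongest reply is that this is loose wording, not a decision to withhold data. A listing of only the pre-worsening visit would serve no purpose, and the word all sits oddly with a single visit. The author may have used OLEXA to mean the extension study, in which case the sentence would be sensible. I think a slip is the likeliest explanation. But the SAP's own definitions tie OLEXA to baseline, nothing in the text signals the other meaning, and a program written to the text would give the wrong listing.

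A reader might infer that the worsening appears in no planned output at all. The documents do not support that: post-OLEXA severity enters both derived parameters and is probably summarised by visit as well. Items 44 and 45 are listed without an OLEXA limit.

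A reader might also infer that the evaluator will have no information on relatedness, impairment or outcome. That is too strong. Adverse event listings carry causality, intensity, duration and outcome (SAP 12.1.1). Causally related TEAEs are summarised (SAP 12.1.5). Adverse event intensity is itself defined by interference with normal activities (Protocol 10.1.2). What remains is that adverse events are a separate capture. Protocol 9.4.10 has them elicited by open questions before PAERS and accepts that the two methods may yield different numbers, so the adverse event listing cannot stand in for the PAERS record.

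Nor do the documents require PAERS relatedness or impairment to be tabulated. The protocol commits to summarising PAERS items, and a severity-based summary meets that.

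Finally, the Data Handling Plan may specify a fuller listing. It could not be checked, so the statement that three fields have no output applies to the protocol and SAP only.

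**Conclusion.** The point stands in limited form. As written, the listing for a worsened PAERS item shows the baseline record (1 of up to 13 scheduled ratings) and none of the up to 12 later ones. For items 1–43, relationship to drug, resolution and functional impairment after OLEXA have no output stated in the protocol or SAP.

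No estimate is biased and no data are lost, since a correct listing can be produced from records already collected. The consequence is a gap in the patient-level evidence for one component of the primary endpoint, in a study whose conclusion rests on clinical review of that evidence. That justifies a correction before the outputs are programmed.

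The conclusion assumes that OLEXA carries the meaning the SAP gives it and that the Data Handling Plan does not already override the sentence.

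**What to change.** Replace the listing sentence in SAP 12.6.2 with wording to this effect:

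> For each patient in whom an item worsens relative to OLEXA, every original record of that item, at OLEXA and at all later scheduled and unscheduled assessments, is listed with severity, resolution, relationship to drug and functional impairment. Worsened records are flagged.

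Check that the Data Handling Plan agrees. While the section is open, also correct the set named for items 44 and 45 (APES), which SAP section 4 does not define.

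The cost is one sentence and a longer listing, with no new data collection. Counts of drug-related or function-impairing worsenings in the worsening table would be an optional extra and are not part of this correction. They would first need a rule for which record counts when a patient worsens at several visits with different ratings.

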### **12.6.3 Tanner Evaluation**

Tanner staging is a scale for assessing physical development and sexual maturity during onset and progress of puberty. The scale includes five stages of pubertal changes (called Tanner stages) separate for males and for females.

For females, the 5 stages of maturation are recognized by assessing pubic hair and breast development. For males, the 5 stages of maturation are recognized by assessing pubic hair, growth of penis and testicles. Post-puberty is defined as a Tanner stage = 5 in both of observed criteria.

Shift tables for the Tanner evaluation displaying shifts from OLEXA to withdrawal/completion will be provided by sex, lead-in treatment and lead-in study, and include the numbers and percentages of patients.

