17.10.2 Analyses of Safety Endpoints

Adverse events, PAERS items, Tanner scores, clinical safety laboratory tests, vital signs, height, weight, BMI, and ECG parameters will be summarised, and observed potentially clinically significant (PCS) safety laboratory test values will be flagged and summarised. Length of menstrual cycle and C-SSRS scores will be summarised using descriptive statistics.

For variables that are heavily dependent on sex and age (such as Tanner and menstrual cycle length) further exploratory descriptions will be made.

Analyses will be performed with respect to the baseline in lead-in study 12709A or 12710A and Baseline Extension A.

For exploratory use a random effects slope and intercept model will be applied using Mixed Model Repeated Measurements (MMRM) to study long-term development in safety parameters such as weight.

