# 2 Study Design

This is an interventional, multi-national, multi-site, open-label, flexible-dose, long-term extension study in child and adolescent patients with MDD who completed one of the double-blind, placebo-controlled, active-reference studies 12709A and 12710A.

The Baseline Visit, hereafter referred to as OLEXA, of this extension study, will be Visit 12 (Completion Visit) of lead-in Study 12709A or 12710A, see section 18.1.

The dosage of vortioxetine will be initiated at 5 mg/day for the first 2 days prior to receiving 10 mg/day. The target dose is 10 mg/day; however, the investigator has the possibility to adjust the dose in case of unsatisfactory response up to 20 mg or in case of dose-limiting adverse events. The dose can be up or down titrated with 5 mg/day. The patient should receive the same dose for 2 days before being up-titrated to a new dose. Changes in dosing may occur at any site visit during the treatment course at the investigator's discretion but the maximum dose may not exceed 20 mg/day.

[figure not shown]
For subset of patients participating in the palatability assessment (patients enrolled in Bulgaria, Estonia, Germany, Latvia, Mexico, Poland, Russia, Serbia, Ukraine, and Colombia), palatability and acceptability of vortioxetine oral drops will be assessed after intake of a single dose (5-20 mg) corresponding to the patient's current vortioxetine dose (instead of their vortioxetine tablet on that day). The assessment can be done at any visit to the clinic from Week 4 to Week 18 (i.e., at Visits 5, 7, 9, or 11).

The treatment period is 26 weeks. The total study duration per patient from OLEXA to the end of follow-up will be approximately 30 weeks.

If possible, patients who withdraw are to be seen for a withdrawal visit as soon as possible and they will be contacted for a safety follow-up visit 4 weeks after withdrawal.

The study design is presented in [Panel 1](#).

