## **4 Analysis Sets**

The following analysis sets will be used to analyse and present the data:

- all-patients-treated set (APTS) – all patients who took at least one dose of vortioxetine in 12712A.
- full-analysis set (FAS) – all patients in the APTS with valid OLEXA assessment and at least one valid post-OLEXA assessment of the CDRS-R total score.

The safety analyses will be based on the APTS. The efficacy analyses will be based on the FAS.

The patients and data will be classified into the analysis sets according to the definitions above after the study database has been released.

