## 9 Exposure and Compliance

Exposure (days) to IMP will be calculated as:

- Date of last dose of IMP – Date of first dose of IMP in study 12712A + 1

Exposure to IMP will be summarized for all patients and by lead-in study and by lead-in treatment using descriptive statistics, and, will include the patient years of exposure (PYE). PYE will be calculated as the sum of the number of days of exposure to IMP for each patient, divided by 365.25 days.

In addition, exposure to IMP will be categorized in intervals (1 – 14 days, 15 – 35 days, 36 – 70 days, 71 – 105 days, 106 – 140 days, 141 – 182 days and >182 – days) and summarized by lead-in study and by lead-in treatment. Missing values of exposure will not be imputed.

Non-compliant days are days on which no IMP has been taken, less than the full dose of IMP has been taken, or more than the full dose of IMP has been taken.

Compliance (%) with IMP will be calculated as:

- $(\text{date of Completion/Withdrawal Visit} - \text{date of Visit 1} - \text{number of days of non-compliance}) / (\text{date of Completion/Withdrawal Visit} - \text{date of Visit 1}) \times 100\%$

where the number of non-compliant days is defined as the sum of all non-compliant days in the treatment period.

Compliance with IMP will be categorized as “≤80% compliant” or “>80% compliant”. The number and percentage of patients in each category will be summarized by lead-in study and lead-in treatment, respectively, by visit interval and for the entire study.

The mean and modal dose of IMP will be calculated for each patient and summarised (mean, median, and lower and upper quartiles for the mean and counts for the modal dose). IMP dose level at the completion or withdrawal of the study will be summarized. Number and percentage of patients who reached highest and lowest dose level will be summarised. In addition, number and percentage of patients with each dose level will be summarised by visit.

Number of patients who exposed to oral drops will be summarized.

Exposure and compliance will be summarized based on the APTS.

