## 17 Changes to Analyses Specified in the Protocol

The following changes have been made as compared to the latest version of the protocol:

- C-SSRS categorisation has been updated and will no longer include C-CASA.
- Treatment emergent adverse events (TEAE) in 12712A is defined as an adverse event that starts or increases in intensity or seriousness after visit 1 of study 12712A.
- The analyses regarding time to first relapse and time to first loss of remission have been removed
- The analysis of random slope and intercept has been removed

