## **Appendix II**

### **Study Flow Chart**

## Study Flow Chart

**Table 1 Study procedures and Assessments**

Visit	Base-line Extension A	Treatment Period												Completion /With-drawal a	Safety Follow-up b
Visit Number	1	2	3	4 c	5	6 c	7	8 c	9	10 c	11	12 c	13	14	
End of Week	0	1	2	3	4	6	8	10	12	15	18	22	26	30	
Visit Window d (days relative to nominal visit)	0 2	± 2	± 2	± 2	± 2	± 2	± 2	± 2	± 2	± 2	± 5	± 5	± 5	± 5	
Baseline Extension A Procedures and Assessments															
Signed informed consent/assent	✓														
Inclusion/exclusion criteria	✓														
Efficacy Assessments															
CDRS-R	✓ e	✓	✓		✓		✓		✓		✓		✓		
CGI-S	✓ e	✓	✓		✓		✓		✓		✓		✓		
CGI-I f	✓ e	✓	✓		✓		✓		✓		✓		✓		
BRIEF (7-11 years at Baseline Extension A)	✓				✓		✓		✓		✓		✓		
BRIEF-SR (12-18 years at Baseline Extension A)	✓				✓		✓		✓		✓		✓		
CGAS	✓ e				✓		✓		✓		✓		✓		
PedsQL VAS (PRO)	✓ e				✓		✓		✓		✓		✓		
Vortioxetine Quantification															
Blood sampling vortioxetine quantification	✓ e				✓								✓		
Safety Assessments															
Adverse events	✓ g	✓	✓	✓	✓	✓	✓	✓	✓	✓	✓	✓	✓	✓ h	
Blood and urine sampling for clinical safety laboratory tests	✓ e,i				✓								✓		
Vital signs	✓ e	✓	✓		✓		✓		✓		✓		✓		
Weight and height	✓ e								✓				✓		
Menstrual cycle and Tanner score	✓								✓				✓		
ECGs	✓ e				✓								✓		
Examinations	✓ e							✓					✓		

Visit	Base-line Extension A	Treatment Period												Completion /Withdrawal a	Safety Follow-up b
		2	3	4 c	5	6 c	7	8 c	9	10 c	11	12 c			
Visit Number	1	2	3	4 c	5	6 c	7	8 c	9	10 c	11	12 c	13	14	
End of Week	0	1	2	3	4	6	8	10	12	15	18	22	26	30	
Visit Window d (days relative to nominal visit)	0	± 2	± 2	± 2	± 2	± 2	± 2	± 2	± 2	± 2	± 5	± 5	± 5	± 5	
(physical and neurological)															
PAERS	✓ e	✓	✓	✓	✓	✓	✓	✓	✓	✓	✓	✓	✓		
C-SSRS	✓ e	✓	✓	✓	✓	✓	✓	✓	✓	✓	✓	✓	✓		
Other Study Procedures															
IMP dispensed	✓	✓	✓		✓		✓		✓		✓		✓		
Possible change in IMP dose		✓	✓		✓		✓		✓		✓		✓		
IMP returned and IMP accountability		✓	✓		✓		✓		✓		✓		✓		

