Recent and concomitant medication	✓ g	✓	✓	✓	✓	✓	✓	✓	✓	✓	✓	✓	✓		
Pregnancy test j	✓ e				✓								✓		
Drug and alcohol screen e,k															

a This visit should take place as soon as possible after the patient withdraws from the study.

b This can be a telephone contact, unless an SAE has occurred since the last visit or unless there was a clinically significant abnormal safety laboratory test value at the last visit. In such cases, safety follow-up(s) must be scheduled to allow for a medical examination and/or blood/urine sampling. Further safety follow-up visits beyond 30 days may be needed as judged by the investigator (if further safety follow-up visits are performed, these must be recorded in the patient's medical record, and not in the eCRF).

c A telephone contact. The patient and/or legal representative and/or the investigator can request an unscheduled site visit to discuss their current dose. During such an unscheduled site visit, the CDRS-R, CGI-S, CGI-I, PAERS and C-SSRS must be performed.

d If the date of a patient visit does not conform to the study plan, subsequent visits should be planned to maintain the visit schedule relative to Baseline Extension A. The number of days between 2 visits must not exceed the number of days for which IMP is provided for in the drug kit.

e Values from assessments and procedures conducted at Visit 12 (Completion Visit) of Study 12709A or 12710A will be the Baseline Extension A Visit values for this study (12712A).

f The assessment of the CGI-I should be in reference to Baseline A in the lead-in studies.

g Ongoing adverse events and concomitant medications (at Completion Visit 12 in Study 12709A or 12710A) will be transcribed to the eCRF Adverse Event Form and Concomitant Medication Form.

h Only for adverse events ongoing at Completion/Withdrawal and new SAEs.

i The 12712A Hormones panel is to be collected using a separate study-specific kit

j Females >10 years of age or female patients at lower age judged by the investigator to be of childbearing potential. Additional pregnancy tests during the study will be performed according to local requirements.

Females <11 years will be tested using a urine hCG test and females >11 years will be tested using a blood hCG test.

- k It is not mandatory to screen for drugs and/or alcohol. However, it can be performed at any visit, at the discretion of the investigator.

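### The Tanner shift tables mix follow-up from days to 26 weeks, and age enters them only through lead-in study

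*SAP*

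**What the plan says.** Tanner score is listed within the primary safety endpoint in Protocol 16.1 and SAP 3.1.

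- **The table.** SAP 12.6.3 says that shift tables "displaying shifts from OLEXA to withdrawal/completion will be provided by sex, lead-in treatment and lead-in study". It sets no minimum follow-up and names no age stratum.
- **The schedule.** In SAP Table 1, the row "Menstrual cycle and Tanner score" is ticked at Baseline Extension A, at Week 12 (read from the column position) and at Completion/Withdrawal. The footnote on that last column says: "This visit should take place as soon as possible after the patient withdraws from the study".
- **Who is included.** Safety analyses use the APTS, defined in SAP 4 as "all patients who took at least one dose of vortioxetine in 12712A".
- **Length of follow-up.** SAP 2 says: "The treatment period is 26 weeks". SAP 9 nevertheless expects very short stays: "exposure to IMP will be categorized in intervals (1 – 14 days, 15 – 35 days", and so on up to more than 182 days.
- **The protocol's commitment.** Protocol 17.10.2 says: "For variables that are heavily dependent on sex and age (such as Tanner and menstrual cycle length) further exploratory descriptions will be made".
- **Declared changes.** SAP 17 opens with "The following changes have been made as compared to the latest version of the protocol". Its four items cover the C-SSRS categorisation, the TEAE definition, the time-to-relapse and loss-of-remission analyses, and the random slope model. None concerns Tanner.

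**The concern.** For most safety variables, harm shows as a change. Slowed puberty shows as no change, and short follow-up puts a patient in the same cell. A table that counts a Week 1 leaver and a Week 26 completer alike therefore understates progression. It can also show differences between lead-in groups that reflect only different withdrawal patterns.

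Age adds to this. Staying at the same stage for six months means different things at different ages, and the study enrols patients from 7 to 18 years. Without age bands, the reader cannot set the observed shifts against what is expected for age. The quantity affected is a component of the primary endpoint.

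**Working it through.** **1. The plan's own figure.** There is none for Tanner. The only planning number is the sample size of about 850, which reproduces: 1200 × 0.80 × 0.85 = 816 and 1200 × 0.85 × 0.85 = 867. It sets the scale and nothing more.

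**2. Who shares a cell.** One dose is enough for the APTS, the withdrawal visit comes soon after withdrawal, and the exposure categories start at 1-14 days. Any early leaver with a withdrawal Tanner score therefore enters the same table as the completers. If stage can only stay or rise, the bias runs one way, towards no shift.

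**3. Size, under assumed rates.** The documents give no progression rate and no withdrawal rate for this study; the 15-20% drop-out figure refers to the lead-in studies. I assume, for patients below stage 5 at OLEXA:
- p26, the share rising at least one stage in 26 weeks: 20%, 30% or 40%
- d, the share withdrawing: 15% to 40%
- a constant rate of progression, the same in leavers and completers
- a Tanner score for every leaver

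Progression by week t is p(t) = 1 − (1 − p26)^(t/26). With withdrawals spread evenly over 26 weeks, the mean among leavers is m = 1 − p26 / [−ln(1 − p26)]. For p26 = 30%, m = 1 − 0.300/0.357 = 15.9%. For 20% and 40%, m is 10.4% and 21.7%. The table would show (1 − d) × p26 + d × m:

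| d | p26 = 20% | p26 = 30% | p26 = 40% | Relative fall |
|---|---|---|---|---|
| 15% | 18.6% | 27.9% | 37.3% | 6.9-7.2% |
| 20% | 18.1% | 27.2% | 36.3% | 9.2-9.6% |
| 30% | 17.1% | 25.8% | 34.5% | 13.7-14.4% |
| 40% | 16.1% | 24.4% | 32.7% | 18.3-19.3% |

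As an extreme, let all withdrawals fall at Week 1. Then p(1) = 1.4% for p26 = 30%, and the table shows 25.7%, 24.3%, 21.4% and 18.5%, which are relative falls of about 14%, 19%, 29% and 38%.

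The leavers' part of the no-shift cells is d(1 − m) / [d(1 − m) + (1 − d)(1 − p26)]. For p26 = 30% with even withdrawal, this is 0.168/(0.168 + 0.560) = 23% at d = 20%, and 0.336/(0.336 + 0.420) = 44.5% at d = 40%.

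**4. Age.** The strata are sex, lead-in treatment and lead-in study. The documents do not give the age range of either lead-in study. They say only that patients could turn 18 during 12710A, which suggests a split into children and adolescents. If that split follows inclusion criterion 1, the strata would span ages 7-11 (five single years) and 12-18 (seven single years), both wide for puberty.

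**5. Protocol against SAP.** Protocol 17.10.2 names two drivers, sex and age, and promises more description. SAP 12.6.3 takes up sex. It neither takes up age directly nor says that it will not, and SAP 17 is silent.

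**The case against.** Several points on the other side are sound, and they rule out stronger readings.

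- **Stage-5 entrants.** A reader might infer that patients already at stage 5 pull down a reported progression percentage. The documents do not support this. A shift table cross-classifies OLEXA stage with end stage, so stage-5 entrants have their own row, and SAP 12.6.3 plans no single share progressing. It does not state the percentage denominator either, so that is worth fixing in words.
- **By-visit output.** A reader might infer that nothing in the plan lets pubertal progression be read. That is too strong. SAP 12.2 asks for safety variables by visit as well as at last assessment, and this may include Tanner. But SAP 12.2 has no age stratum and promises no stage-by-stage shift at Week 26. How withdrawal scores are assigned to visits is left to a Data Handling Plan that is not among the documents.
- **Age.** A reader might infer that age is ignored altogether. Lead-in study is probably a rough age split, and conditioning on OLEXA stage separates some ages too. What stands is that the proxy is coarse and its age limits are unstated.
- **The protocol's promise.** A reader might infer that a specified age-band analysis was deleted. Protocol 17.10.2 promises exploratory description without bands or method. The gap is an unfulfilled and undeclared commitment, not a removed table.
- **Size.** Every rate above is assumed. Protocol 8.4 has leavers attend the withdrawal visit only where possible; those who do not attend have no withdrawal score, which lessens the dilution. SAP 6.2 and SAP 9 will show how much early withdrawal occurred in each group, though not which Tanner cells it fills.
- **No control.** Everyone takes vortioxetine. Even a better table cannot establish delay by itself.

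**Conclusion.** The point holds in a limited form. The SAP 12.6.3 tables mix follow-up from days to 26 weeks, and this biases apparent progression towards no shift. Age is represented only by lead-in study, despite the protocol's naming of Tanner in 17.10.2, and SAP 17 does not declare the omission.

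The direction of the bias rests on stage not falling. Its size rests on rates the documents do not give: about 7-19% in relative terms with even withdrawal of 15-40% and true progression of 20-40%, and about 14-38% if all withdrawals came at Week 1. At the milder end the effect is modest. The change is worth making because it concerns a primary-endpoint component and uses data already scheduled, not because the planned output is without value. Any inference about pubertal delay will still need an age-specific reference.

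**What to change.** In SAP 12.6.3:

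1. Tabulate shifts from OLEXA to Week 12 and from OLEXA to Week 26, each among patients assessed at that time.
2. Show shifts at withdrawal visits separately, by time on study. Because the Week 26 table is then restricted to those who stayed, the two should be presented together.
3. Compute percentages within OLEXA stage, so that stage-5 entrants are in no progression denominator.
4. Add broad bands of age at OLEXA (for example two-year bands) by sex, pooled over lead-in treatment. Otherwise, list the departure from Protocol 17.10.2 in SAP 17.
5. State that without a concurrent control the tables need an age-specific reference before delay is inferred.

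The cost is SAP wording and table programming; no visit or assessment changes. The downside is some small cells. Ages 7 to 18 make six two-year bands, so 2 sexes × 6 bands × 5 stages = 60 cells, an average of 850/60 ≈ 14 patients before any loss to withdrawal. Single-year bands would give 120 cells of about 7. In practice patients will be unevenly spread, and sparse cells may need merging.
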